#### 2. Out of clinic assessments:

- a. ViMove Monitoring- All day (out of clinic) monitoring assessment of:
  - i. Peak angle ROM
  - ii. Total ROM score
  - iii. Total dynamic time over the monitoring period
  - iv. Body orientation summary over monitoring session (% time spent sitting, standing, horizontal, dynamic)

### **6: STUDY POPULATION**

20 participants will be recruited from each arm of the study, resulting in a total of 40 valid subjects. Although we will initially recruit 50 subjects, we expect an attrition rate of 20%.

### 7: ELIGIBILITY CRITERIA

### 7.1 Inclusion Criteria

There are two respective sets of inclusion criteria which subjects from each study arm must meet to be eligible for the study:

# 7.1.1 Inclusion Criteria for Low Back Pain Patients:

- 1. Males and Females between the age of 21-54 inclusive.
- 2. Low back pain is the primary source of pain over the last 3 weeks.
- 3. Have experienced and received treatment for muscle related low back pain over the past 3 weeks with an average score of at least 3/10 on a 10-point Numeric Rating Scale.
- 4. Must be able to communicate fluently in English.
- 5. Must provide written informed consent.
- 6. Must agree to confidentiality.

# 7.1.2 Inclusion Criteria for Active in Sport:

- 1. Adults between the age of 21-54 inclusive, male and female.
- 2. Participate in 30 min of moderate to high intensity exercise 3 times per week.
  - Intensity is assessed using the Borg Rating of Perceived Exertion (RPE)
- 3. Must be able to communicate fluently in English.
- 4. Must provide written informed consent.
- 5. Must agree to confidentiality.

### 7.2 Exclusion Criteria

Potential subjects who meet any of the following criteria will not be eligible for participation in this study:

- 1. The subject is pregnant.
- 2. The subject has a severe hearing impairment or an inability to follow verbal instructions in English.
- 3. The subject is cognitively impaired.
- 4. Known allergic skin reaction to tapes and plasters.
- 5. Co-morbidities of neoplasm, infection, fracture, inflammatory or metabolic disorder that has potential to affect the lumbo-pelvic region.
- 6. Preceding chronic myelopathy, specific neurological disease or neurological changes.
- 7. Person who is currently enrolled in another investigational drug or device study.
- 8. Any past or current heart or blood-circulation related disorders.
- 9. The subject is contraindicated for this study for any other reason.

### 7.3 Withdrawal Criteria

The following are a list of reasons for participants to be discontinued from the trial by the Investigator:

- 1. Withdrawal of Participant's consent.
- 2. Failure to maintain an adequate level of compliance with wearing sensors.
- 3. Failure to co-operate adequately with the Principal Investigator or staff during clinical visits.
- 4. Failure to adequately adhere to protocol requirements within or outside the clinical environment.
- 5. Participant experiences a serious adverse event (see section 10)
- 6. Participant no longer meets the inclusion criteria (see section 7.1)
- 7. Pregnancy.

### 8: STUDY PROCEDURES

### 8.1 Recruitment of Subjects

Two discrete groups of people will participate in this study.

- 1. The first group will be comprised of patients who have experienced and/or received treatment for low back pain within the past 3 weeks. This group will be recruited from private physiotherapy clinics.
- 2. The second group will be comprised of people who participate in 30-minutes of moderate-to-high intensity exercise 3-times per week. This group will also be recruited from private physiotherapy clinics.

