#### **Inclusion Criteria:**

#### Inclusion criteria for recent low back pain patients:

- 1. Adults between the age of 21-54 inclusive, male and female.
- 2. Low back pain is the primary source of pain over the last 3 weeks.
- 3. Have experienced and/or received treatment for muscle related low back pain with an average score of at least 3/10 on a 10-point Numeric Rating scale over the past 3 weeks.
- 4. Must be able to communicate fluently in English.
- 5. Must provide written informed consent.
- 6. Must agree to confidentiality.

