## 2: BACKGROUND

Low Back Pain (LBP) is common in the general population with a 12-month point prevalence of 12% and 1-month prevalence of 23% [1]. Nonspecific LBP, the most common presentation, is defined as pain of unclear pathology below the costal margin and above the inferior gluteal folds [2-5]. Although the prognosis for LBP appears to be favorable, rates of chronicity are high [6] with previous LBP being a strong risk factor for ongoing complaint or relapse [7]. This makes LBP one of the leading causes of years lived with disability in developed countries [8], resulting in direct and indirect costs of \$84.1 to \$624.8 billion in the United States [9]. As such, addressing LBP effectively is necessary to minimize the associated physical and financial burden [10].

There are numerous proposed methods to treat LBP. Effective interventions include spinal manipulation, and medications such as painkillers [11, 12]. However, these interventions can be invasive and are associated with extensive time requirements, high costs, and adverse side effects [13, 14]. Thus, non-invasive and easy-to-administer treatments such as heat therapy may be preferred, although their effectiveness is not as consistent [12, 15]. One such heat therapy is in the use of ThermaCare HeatWraps (Pfizer Consumer Healthcare, Richmond, VA). ThermaCare is a brand of non-invasive disposable heat wraps which provide the wearer with continuous low-level direct heat therapy for approximately 8 hours. ThermaCare HeatWraps are customized for specific parts of the body, including the low back. Clinical trials have demonstrated the efficacy of this intervention in the early treatment and prevention of Delayed Onset Muscle Soreness (DOMS) [5, 16]. Moreover, ThermaCare has been shown to be effective in the prevention of post-exercise pain and muscle soreness [16, 17]. Compared with the pain relievers ibuprofen and acetaminophen, ThermaCare provided more effective pain relief, and significantly improved flexibility and disability [18].

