# 8.4 Methodology

The following tasks will be conducted on the recruitment day (Day 0) for all subjects, and will be recorded in each subject's respective source documents and case report forms (CRFs):

- 1. Assessment of eligibility against inclusion and exclusion criteria
- 2. An explanation of study procedures.
- 3. Provision and obtainment of written informed consent.
- 4. Obtainment of demographic information and medical history.
- 5. Booking of Day 1 and Day 2 (based on convenience).

The main study will be conducted over 2 consecutive days for each subject.

Participants will be asked to complete each of the following - 30 minutes prior to their appointment on Day 1; the Oswestry Disability Index (ODI), a Numeric Rating Scale for Pain (NRS Pain), the Roland Morris Disability Questionnaire, and a Low Back Pain Classifier.

Both subject groups will then have a "start interview" on their allocated baseline assessment day (Day 1). This will include fitting of the ViMove movement and EMG sensors, as well as a ViMove live "pain on movement" assessment. This session will take approximately 20-30 minutes. Whilst wearing the ViMove sensors, subjects will then leave the clinic and conduct normal daily activities for a predetermined monitoring period. No ThermaCare HeatWraps are worn on Day 1. This allows a baseline assessment and allows any placebo effects from the sensors to be discounted. At the end of the monitoring session, subjects will return to the clinic to have an "end-of-day" interview. Participants will complete a Patient Global Impression of Change scale (PGIC), a repeat NRS, and will have another live ViMove assessment. Movement sensors will then be removed, and the subject will be reimbursed for that day.

The intervention day (Day 2) will have the same procedure as Day 1 (baseline), with the only difference being the additional application of ThermaCare HeatWraps during the "start interview". ThermaCare will only be applied after the live assessment, so will not be worn at the same time as the EMG sensors. Subjects will continue to wear the HeatWrap and ViMove sensors during the 8-hour daily activity monitoring period, with the wrap and sensors being removed during the end-of-day interview, prior to the end-of-day live assessment. The subject will then be reimbursed for Day 2. A schedule of events can be seen in Table 1, and a summary of the procedure can be seen in Figure 1.

Table 1. Schedule of Events

[figure not shown]

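### No booking rule, record or analysis step deals with non-drug back treatment on the two study days, so treatment of a Group 1 subject on one day only can bias the result, for or against heat

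*Combined protocol and SAP*

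**What the plan says.** **Who is recruited.** Section 8.1 defines Group 1 as patients who have experienced low back pain and/or "received treatment for low back pain within the past 3 weeks. This group will be recruited from private physiotherapy clinics". The Protocol Summary has the same optional wording: "Have experienced and/or received treatment for muscle related low back pain with an average score of at least 3/10". Section 7.1.1 instead makes treatment a condition of entry: "Have experienced and received treatment for muscle related low back pain over the past 3 weeks".

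**When and where they are seen.** The first appointment is made within 3 weeks of enrolment at the subject's preferred clinic (8.3.1). The two days are consecutive, and the scheduling rule in 8.4 is "Booking of Day 1 and Day 2 (based on convenience". Each day has a start and an end visit: Visits 2 and 3 on Day 1, Visits 4 and 5 on Day 2.

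**What separates the days.** Section 8.4 gives Day 2 the same procedure as Day 1, "with the only difference being the additional application of ThermaCare HeatWraps". The wrap goes on after the Visit 4 live assessment and comes off before the Visit 5 one.

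**What is restricted, recorded or analysed.** None of the nine exclusions (7.2) or seven withdrawal reasons (7.3) mentions physical treatment or other heat products. Table 1 has a row for changes in medications at Visits 2 and 4 and no row for other treatment. Section 11.2 plans one Wilcoxon signed-rank test for Baseline and one for Intervention, then a repeated measures ANOVA on post-trial data, with no step for co-treatment.

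**The concern.** The study has no control arm. The no-wrap Day 1 is its only guard against reading other influences as heat, and it works only for influences common to both days. Treatment that falls on one day is not common to both.

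The protocol itself regards such treatment as active: "Effective interventions include spinal manipulation, and medications such as painkillers" (section 2). Group 1 is drawn from places that deliver back treatment. Section 9.1 also sends ViMove data to a treating clinician, so contact with one is foreseen. The primary endpoints (range of motion, flexion-relaxation response, pain during movement) are ones that physical treatment may plausibly change. Because the schedule does not ask about it, such treatment could not be identified afterwards, and the estimates carried into the planned RCT would include it.

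**Working it through.** **Plan's own figure.** The documents give no session rate or treatment effect, so no figure on this point can be reproduced. The group size used below is theirs: 20 per group, 40 in total, and 40/(1 − 0.20) = 50 recruited, which matches section 11.1.

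**Step 1: where a session enters.** Write Y2 to Y5 for the outcome at Visits 2 to 5. Let a session improve it by *s* with no fading, and let heat do nothing. I read the post-trial data of 11.2 as the end-of-day values, so that comparison is Y5 − Y3.

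| Session falls between | Day 1 change Y3 − Y2 | Day 2 change Y5 − Y4 | Post-trial Y5 − Y3 | Day 2 change minus Day 1 change |
|---|---|---|---|---|
| Visits 4 and 5 | 0 | +s | +s | +s |
| Visits 3 and 4 | 0 | 0 | +s | 0 |
| Visits 2 and 3 | +s | 0 | 0 | −s |

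If the effect fades, a session between Visits 3 and 4 makes the Day 2 change slightly negative, and a Day 1 session makes Y5 − Y3 negative. The subject's own heat product behaves in the same way; 8.4 rules out ThermaCare on Day 1 but says nothing of other products.

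**Step 2: how often (illustration).** Assume every Group 1 subject is in treatment, with sessions falling at random on distinct days of a 5-day working week.

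- One session a week, on Day 2: 1/5 = 20%, or 0.20 × 20 = 4 subjects.
- Two a week, on Day 2: 2/5 = 40%, or 0.40 × 20 = 8 subjects.
- One a fortnight, on Day 2: 1/10 = 10%, or 0.10 × 20 = 2 subjects.
- Treatment ended: 0.
- On either study day, one a week: 2/5 = 40% (8 of 20). Two a week: 1 − C(3,2)/C(5,2) = 1 − 3/10 = 70% (14 of 20).

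Spreading sessions over 7 days instead gives 20 × 1/7 = 2.9 to 20 × 2/7 = 5.7 subjects on Day 2. All Day 2 counts include sessions before Visit 4 or after Visit 5, which do not enter the Day 2 change directly.

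**Step 3: effect on the Day 2 test (illustration).** Two-sided signed-rank test, n = 20, normally distributed changes, no heat effect, 4,000 simulated trials. Each affected session is assumed to fall between Visits 4 and 5 and to shift the change by 0.5 to 1.0 SD.

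| Share affected | Mean spurious change (share × shift) | Significant in favour of heat |
|---|---|---|
| 0 | 0 | about 2% |
| 1/7 | 0.07 to 0.14 SD | 4% to 8% |
| 2/7 | 0.14 to 0.29 SD | 9% to 18% |

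**The case against.** The strongest reply is that the damaging window is also the least likely one. Between Visits 4 and 5 the subject wears lumbar sensors and the wrap for 8 hours, hands-on treatment would tend to disturb them, and poor sensor compliance is a withdrawal reason. A session just before Visit 4 is in the starting value, and one after Visit 5 is irrelevant. This stands: it is why the Day 2 counts are an upper range. It does not close the gap, since no text excludes treatment then and other forms of therapy or own heat remain possible.

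Four stronger readings are tempting, and the documents do not support them.

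- *That all of Group 1 are in continuing physiotherapy.* Only 7.1.1 requires treatment, no passage says it was physiotherapy, and treatment in the past 3 weeks need not be continuing.
- *That the plan claims nothing else differs between the days.* The sentence in 8.4 describes study procedures, not the rest of the subject's day.
- *That any session near Day 2 is credited to heat.* Step 1 shows one window that favours heat in every comparison, one that is mostly absorbed, and one that tends to work against it.
- *That convenience booking raises the overlap.* The protocol does not say that study visits are combined with treatment appointments.

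It is also fair that this is a feasibility study meant to guide an RCT. That lowers the stakes of a false positive, but how often co-treatment occurs is something a pilot should find out. The catch-all exclusion and the general adherence rule do not help, because there is no co-treatment requirement to breach.

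**Conclusion.** The gap is real: in the text available, non-drug back treatment and other heat products on the study days are not prevented, recorded or handled in the analysis. The bias can go either way, and the case that favours heat directly is a session between Visits 4 and 5.

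The size cannot be fixed from the documents. At an assumed one or two sessions a week for every subject, 20% to 40% (4 to 8 of 20) would have a session on Day 2. This bounds the direct effect from above under that assumption, and the share falls to 10% at one session a fortnight and to zero if treatment has ended. The 40% and 70% figures pool both days and should not be read as the share credited to heat. The false-positive rates in Step 3 rest on assumed shifts and timing and show direction and order of size only.

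The conflict over whether prior treatment is required must be reconciled, but the gap exists under either wording. Section 5 (study setting) and Figure 1 could not be read for this check; a booking or co-treatment rule there would narrow the point. The matter should be corrected; it does not invalidate the feasibility aim.

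**What to change.** 1. In 8.4, replace booking by convenience with: choose two consecutive days with no low back treatment session already planned between the start of Visit 2 and the end of Visit 5. Care itself is unchanged; the study days move around it.
2. Add a row to Table 1 and a CRF question at Visits 2 to 5 on any physical treatment or other heat product since the last visit; at Visit 2, record the date of the last treatment. A session shortly before Visit 2 stays possible, but becomes visible.
3. In 11.2, prespecify a repeat of the Group 1 analysis without affected subjects, and report how many there were.
4. Reconcile the treatment wording in 7.1.1 with 8.1 and the Protocol Summary.

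The cost is one sentence, one question at existing visits and one extra analysis. Scheduling within the 3-week window becomes slightly less flexible, and the sensitivity analysis has a smaller n. Recording alone would be weaker: at the Step 2 rates, dropping subjects treated on either day would leave 20 − 8 = 12 or 20 − 14 = 6, so the booking rule is what keeps that analysis usable.

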#### 8.2 Randomization

This study has been designed as an initial feasibility study providing insights that would guide an RCT. As such, this is a non-randomized partially blinded study, as the investigator and participants will be blinded to ViMove results, but not the test condition. Groups will not be randomized, and will be based on recruitment.

# **8.3 Study Protocols**

### 8.3.1 Guidelines for Scheduling Subjects' Clinic Visits

Following enrolment into the study, an appointment is made for the subject within 3 weeks at their preferred clinic to begin the assessment.

# 8.3.2 Study Personnel Training

All personnel performing the ViMove fitting and assessment will undergo a training program in the use of the devices.

# 8.4 Methodology

The following tasks will be conducted on the recruitment day (Day 0) for all subjects, and will be recorded in each subject's respective source documents and case report forms (CRFs):

- 1. Assessment of eligibility against inclusion and exclusion criteria
- 2. An explanation of study procedures.
- 3. Provision and obtainment of written informed consent.
- 4. Obtainment of demographic information and medical history.
- 5. Booking of Day 1 and Day 2 (based on convenience).

The main study will be conducted over 2 consecutive days for each subject.

Participants will be asked to complete each of the following - 30 minutes prior to their appointment on Day 1; the Oswestry Disability Index (ODI), a Numeric Rating Scale for Pain (NRS Pain), the Roland Morris Disability Questionnaire, and a Low Back Pain Classifier.

Both subject groups will then have a "start interview" on their allocated baseline assessment day (Day 1). This will include fitting of the ViMove movement and EMG sensors, as well as a ViMove live "pain on movement" assessment. This session will take approximately 20-30 minutes. Whilst wearing the ViMove sensors, subjects will then leave the clinic and conduct normal daily activities for a predetermined monitoring period. No ThermaCare HeatWraps are worn on Day 1. This allows a baseline assessment and allows any placebo effects from the sensors to be discounted. At the end of the monitoring session, subjects will return to the clinic to have an "end-of-day" interview. Participants will complete a Patient Global Impression of Change scale (PGIC), a repeat NRS, and will have another live ViMove assessment. Movement sensors will then be removed, and the subject will be reimbursed for that day.

The intervention day (Day 2) will have the same procedure as Day 1 (baseline), with the only difference being the additional application of ThermaCare HeatWraps during the "start interview". ThermaCare will only be applied after the live assessment, so will not be worn at the same time as the EMG sensors. Subjects will continue to wear the HeatWrap and ViMove sensors during the 8-hour daily activity monitoring period, with the wrap and sensors being removed during the end-of-day interview, prior to the end-of-day live assessment. The subject will then be reimbursed for Day 2. A schedule of events can be seen in Table 1, and a summary of the procedure can be seen in Figure 1.

Table 1. Schedule of Events

[figure not shown]
Tuble 1: Senedale of Events	Visit 1*	Visit 2*	Visit 3	Visit 4	Visit 5
		Baseline	Baseline	Intervention	
	(Day 0) Enrol-	Baseline Start	End of	Start	Intervention End of Day
		Interview		Interview	Interview
	ment		Day	interview	interview
		(within 3 weeks of	Interview		
		Visit 1)			
Eligibility	х				
Informed consent	х				
Demographics & Medical History	Х				
Enrolment and scheduling	Х				
Questionnaires		x		x	х
ViMove application		х		х	
ViMove in clinic assessment		х	Х	х	Х
ViMove monitoring assessment		х		х	
ViMove removal			Х		Х
ThermaCare application				х	
ThermaCare removal					Х
Adverse Events		х	Х	х	Х
Changes in medications		х		х	
Study Termination					х

\*Baseline may occur on the same day as Visit 1 (i.e. enrolment).

Subjects who withdraw from the study after providing informed consent are referred to as "dropouts" or premature withdrawals. The drop-out rate will be summarized. If the patient has provided a whole set of Day 1 data, this will be included in the study.

We expect 6-months will be required from first participant enrolment to the last participant visit. A further 3-months will be required for analysis and write-up.

Figure 1. Summarized Procedure

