# 3: AIMS, HYPOTHESES, AND OBJECTIVES

#### **3.1** Aims

The aims of this study are to evaluate the efficacy of ThermaCare HeatWraps:

- 1. As an intervention for people with low back pain.
- 2. As an intervention for people who are actively involved in sport.

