### 4: STUDY DESIGN

This investigator-initiated study will utilize a prospective open-label study design. This allows the assessment of ThermaCare HeatWrap efficacy pre- and post- intervention, and may provide insight into the mechanisms of any observed pain relief. The nature of the ThermaCare intervention means that blinding is difficult, as there is no adequate placebo heat therapy.

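### Heat always follows a no-heat day, and no between-day contrast of change is planned, so sensor effects are not discounted and efficacy cannot be evaluated as claimed

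*Combined protocol and SAP*

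**What the plan says.** **Sequence.** Under 8.4, "The main study will be conducted over 2 consecutive days for each subject". On the first day, "No ThermaCare HeatWraps are worn on Day 1". The second day repeats the first, "with the only difference being the additional application of ThermaCare HeatWraps". Table 1 places an in-clinic ViMove assessment at the start and end of each day (Visits 2 to 5). On Day 2 the wrap goes on only after the start-of-day assessment, so Visit 4 is heat-free.

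**Controls.** Section 4 explains that blinding is difficult "as there is no adequate placebo heat therapy". Section 8.2 says that the study is not randomised and that neither participants nor the investigator are blinded to the test condition. Both populations receive heat on Day 2, so neither serves as a concurrent control.

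**Claims.** Section 8.4 says of Day 1: "No ThermaCare HeatWraps are worn on Day 1. This allows a baseline assessment and allows any placebo effects from the sensors to be discounted". Section 3.1 states: "The aims of this study are to evaluate the efficacy of ThermaCare HeatWraps". Section 3.2 hypothesises effectiveness in each population. Section 8.2, however, says: "This study has been designed as an initial feasibility study providing insights that would guide an RCT", and 11.1 gives feasibility as the reason for the sample size.

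**Analysis.** Section 11.2 plans Wilcoxon signed-rank tests of movement, one for Baseline and one for Intervention. A repeated measures ANOVA on post-trial data for the two groups follows. Any p-value below 0.05 counts as significant. The section does not name the visits compared, and it names no contrast between the Day 1 change and the Day 2 change.

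**The concern.** A no-heat day can discount the effect of wearing sensors only if its change is subtracted from the change on the heat day. Section 11.2 does not do this. It yields two p-values, and the natural use of them is to see whether Intervention is significant and Baseline is not. That comparison does not test whether the two changes differ.

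Even with the right contrast, anything other than heat that acts differently on the second day is counted as heat. Candidates are a different practice effect on repeated movement tests, recovery in Group 1 (recent back pain averaging at least 3/10 over three weeks), and expectation raised by a wrap that subjects know they are wearing. The documents mention neither order, practice nor recovery.

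At stake are the conclusion on effectiveness and the change estimate carried forward to plan the RCT.

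**Working it through.** **Plan's own figure.** The only derived number is recruitment: 40 / (1 − 0.20) = 50, as stated in 11.1. It is correct and unaffected. The documents give no SD, effect size or power, so every drift size below is an assumption.

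**What the four assessments identify.** Let μ be the Visit 2 mean, d a constant shift between days, s a start-to-end change common to both days (including an equal sensor effect), h the heat effect, and x any non-heat change within Day 2 beyond s.

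| Visit | Mean |
|---|---|
| 2 (Day 1 start) | μ |
| 3 (Day 1 end) | μ + s |
| 4 (Day 2 start) | μ + d |
| 5 (Day 2 end) | μ + d + s + h + x |

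- Intervention test, read as Visit 5 − Visit 4: s + h + x. The between-day shift d cancels, but s does not.
- Baseline test, read as Visit 3 − Visit 2: s.
- Contrast (Visit 5 − Visit 4) − (Visit 3 − Visit 2): h + x. Both d and s cancel.
- Visit 4 − Visit 2: d only. This says nothing about s or x.

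A model with intercept, day, end-of-day and heat (Visit 5 only) has rank 4 of 4, so d and s are separable from heat. A column for x is identical to the heat column, so the rank stays at 4 of 5. No sample size separates h from x.

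**Size of the side-by-side problem.** Inputs are n=20 per group (11.1), alpha 0.05 (11.2; two-sided assumed) and h = x = 0. Within-day changes are normal with SD 1, and the two days are simulated as independent. If one Wilcoxon test is significant with probability p, then P(Day 2 significant, Day 1 not) = p(1 − p).

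| Common drift s | p | p(1 − p) | Simulated directly | Contrast test |
|---|---|---|---|---|
| 0 | 0.048 | 0.046 | about 5% | about 5% |
| 0.3 SD | 0.239 | 0.239 × 0.761 = 0.182 | 17–18% | about 5% |
| 0.5 SD | 0.546 | 0.546 × 0.454 = 0.248 | 25–26% | about 5% |

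Positive correlation between a subject's two daily changes would make the tests agree more often and lower the two drift rows.

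**What the contrast leaves.** With independent days its SD is √2 = 1.41. An extra Day 2 non-heat change x of 0.3 or 0.5 SD is therefore 0.3/1.41 = 0.21 or 0.5/1.41 = 0.35 contrast SDs. With no heat effect, the contrast is significant in about 14–15% or 31–32% of simulated trials.

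**The case against.** The strongest reply is that this is an openly uncontrolled pilot. The title calls it one, 8.2 and 11.1 state a feasibility purpose, Section 4 admits that there is no placebo heat, and 13.1 to 13.3 speak of change, not proof. All of that stands. Nothing is concealed, and an uncontrolled pilot is a legitimate design. It does not rescue the sentence in 8.4 or the aims in 3.1 and 3.2, which assert more than that purpose needs.

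A second reply is that the ANOVA might supply the missing comparison. Section 11.2 does not define post-trial data. If the ANOVA compares the two end-of-day readings, it estimates Visit 5 − Visit 3 = d + h + x, which keeps the between-day shift and is not the contrast of change.

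Four stronger readings are tempting, and the documents do not support them:

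- A reader might infer that the plan claims to discount placebo effects in general. Section 8.4 limits the claim to effects from the sensors.
- A reader might infer that fixed order makes day and heat wholly inseparable. That would hold with one reading per day. With Visits 2 to 5, a constant day shift and a common within-day drift can be separated.
- A reader might take the chance that one paired test is significant under an assumed shift (13%, 23% or 55% at 0.2, 0.3 or 0.5 SD) as the bias from fixed order. Those figures hold for any paired test with a shift inside the tested interval.
- A reader might take the Visit 2 to Visit 4 difference as the yardstick for the heat-day change. It measures d, which Visit 5 − Visit 4 already removes, so a small value would reassure falsely.

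Two limits also belong here. Recovery concerns Group 1, over two consecutive days; the sport criteria require no pain. Practice could act in either direction: if most learning occurs at the first repetition, on Day 1, the contrast would understate heat.

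**Conclusion.** The plan is wrong as written on two counts. First, the 8.4 statement about sensor effects is not delivered by 11.2, because no between-day contrast of change is named. With the contrast it would hold only if the sensor effect is the same on first and second wear. Second, the efficacy language of 3.1 and 3.2 cannot be supported, because Day 2-specific practice, recovery or wrap expectation cannot be separated from heat by any analysis of these data.

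The first fault can be repaired from data already planned: about 17–18% or 25–26% misleading patterns at a common drift of 0.3 or 0.5 SD fall to about 5%. The second can only be acknowledged. These rates rest on assumed drifts, normal changes, independent days, n=20 per group and the natural reading of the Wilcoxon tests as within-day. They illustrate size and are not estimates for this trial. The documents do not show that a non-heat effect will occur, nor that the results will be reported as proof of effectiveness.

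**What to change.** 1. **Section 11.2.** Make the heat-day comparison the within-person contrast (Visit 5 − Visit 4) − (Visit 3 − Visit 2), by group, with a 95% CI, in place of reading the two within-day tests side by side. The Visit 2 to Visit 4 difference may be reported, but only as a description of between-day shift. The in-clinic ViMove measures needed are already scheduled at all four visits. For the contrast to be fair, the two monitoring periods should be comparable in length; 8.4 gives 8 hours for Day 2 but only a predetermined period for Day 1, so this should be clarified.
2. **Section 8.4.** Qualify the sentence: sensor effects are removed only through that contrast and only if they are equal on both days, and wrap expectation is not controlled.
3. **Sections 3.1, 3.2 and the study conclusion.** Restate these as estimating change on the heat day in order to plan an RCT, not as showing efficacy, in line with 8.2 and 11.1. The same efficacy wording in Section 4 and the Protocol Summary should follow.

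**Cost.** This is wording plus one analysis of planned data, with no new visit or procedure. The claim becomes more modest. The interval is likely to be somewhat wider: the contrast has SD √(2(1 − ρ)) times that of a single-day change, where ρ is the between-day correlation and the daily SDs are equal. That is 1.41 times at ρ = 0 and no wider at ρ = 0.5.
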